## 1.3 Potential Risks to Human Subjects

Assessments, including measurement of IOP and outflow facility pose a minimal risk of corneal abrasion, similar to that of a routine eye exam. Phase 1 through Phase 3 safety data

indicate that there is minimal risk involved in a short (7 day) course of netarsudil, and treatment with placebo in one eye is of sufficiently short duration to not be considered a risk for disease progression. Please refer to the [Investigators' Brochure](#) for more detailed information on potential risks.

Previous animal ([AR-13324-APH07](#)) and human ([AR-13324-CS102](#), and [AR-13324-CS201](#)) studies indicate a minimal contralateral effect, thus suggesting that the paired-comparison design is appropriate.

## **2. STUDY OBJECTIVES**

### **2.1 Primary Objective(s)**

The primary objective of this study is to evaluate the effect on trabecular outflow facility of netarsudil ophthalmic solution 0.02%, compared to placebo, in subjects with POAG or OHT.

### **2.2 Secondary Objective(s)**

To evaluate the effect on IOP and EVP of netarsudil ophthalmic solution 0.02% compared to placebo in subjects with POAG or OHT.

To evaluate the ocular and systemic safety of netarsudil ophthalmic solution 0.02%.

### 3. INVESTIGATIONAL PLAN

#### 3.1 Overall Study Design and Plan

This will be a double-masked, placebo-controlled, paired-comparison study conducted at approximately 2 centers in the US to evaluate the effect of treatment with netarsudil ophthalmic solution 0.02% (netarsudil) on trabecular outflow facility. Netarsudil will be administered to one eye and Placebo to the contralateral eye once daily, 1 drop in the morning (QD, AM), in adult subjects at least 18 years of age with primary open angle glaucoma (POAG) or ocular hypertension (OHT). Study medication will be administered for 7 consecutive days, although the total time of subject participation in the study (including washout from prior treatment, if necessary) may be up to 7 weeks.

Subjects will be eligible to enroll in the study if they have a current diagnosis of POAG or OHT in both eyes (POAG in one eye and OHT in the contralateral eye is also acceptable), and may be treatment-naïve or taking topical ocular hypotensive medication. If necessary, subjects who agree to participate in the study will be required to washout from their current intraocular pressure (IOP)-lowering treatment for a minimum specified period of time (5 days to at least 4 weeks), according to the type of treatment. Subjects will attend a total of 3 study visits: a screening visit (Visit 1), to be conducted up to 6 weeks prior to a qualification visit (Visit 2, Day 1, baseline), and a final visit after 6 days on-treatment (Visit 3, Day 8, exit) where a member of the site staff will administer their 7th dose after completing their 08:00 hour assessments.

Both eyes must qualify for the study with an unmedicated (post-washout or treatment-naïve) IOP of >20 mmHg but <30 mmHg at 08:00 hours and >17 mmHg but <30 mmHg at 13:00 and 16:00 hours at the qualification visit. In order to be randomized into the study, eligible subjects must meet all of the inclusion, and none of the exclusion criteria at both the screening and at the qualification visit, following washout from their current ocular hypotensive treatment, if required.

If the subject continues to be eligible, they will be randomized at the end of their qualification visit (Visit 2, Day 1, baseline) to receive netarsudil ophthalmic solution 0.02% in one eye and Placebo in the contralateral eye for 7 days, QD (AM). Subjects will be asked to begin self-administration of their assigned medications in the morning on Day 2 following their baseline (Day 1) visit. Subjects will be instructed to administer 1 drop from each bottle of their study medication into the assigned eye for that bottle, every morning at approximately the same time (between 08:00 and 10:00 hours) for 6 consecutive days. On the day of the final (exit) visit (Visit 3, Day 8), subjects will return to the site at 08:00 hours for their final dose of study medication and to complete their on-treatment measurements before exiting.

Safety measures (including visual acuity, biomicroscopy, and AEs) will be evaluated at all visits. Efficacy assessments will include IOP at 08:00, 13:00 and 16:00 hours, and trabecular (tonographic) outflow facility and EVP, which will be measured at 13:00 and 16:00 hours. Tonographic outflow facility (primary endpoint) and IOP (secondary endpoint) will be

collected in all subjects. The other secondary endpoint, EVP, will be measured in a subset of subjects.

### **3.2 Rationale for Study Design and Control Group**

The primary treatment effect of netarsudil 0.02% is lowering IOP in subjects with glaucoma or OHT. From the results of mechanism of action studies conducted in both rabbits and monkeys, netarsudil is believed to lower IOP by several mechanisms including increasing aqueous humor outflow via the trabecular meshwork, reducing EVP and reducing aqueous humor production. Based on results from the Phase 1 study in healthy volunteers (AR-13324-CS102), the current study is designed to evaluate trabecular outflow facility, EVP and IOP in response to treatment with netarsudil ophthalmic solution 0.02% compared to placebo in subjects with elevated IOP.

The current design is powered on the most clinically-relevant component of AHD, trabecular outflow facility, thought to be the primary mechanism of action of netarsudil in lowering IOP.

Since the study treatment period is short (7 days), there is not believed to be a significant risk to subjects of the paired comparison design (i.e. active treatment in one eye and placebo in the fellow eye). Additionally, washing-out from their prior ocular hypotensive therapy, if necessary, should not pose a significant risk of clinically-relevant disease progression, since subjects will only be on investigational treatment or placebo for 7 days then can revert to their prior IOP-lowering treatment.

### **3.3 Study Duration and Dates**

The duration of treatment in this study is 7 consecutive days following randomization. Subjects will begin dosing on Day 2, in the morning following their Day 1 (qualification/baseline) visit, and dose for the next 6 days, returning to the site on Day 8 where their 7th and final dose will be administered. Subjects that are taking ocular hypotensive treatments at Screening will be required to wash-out of their current treatments as specified in [Table 1](#).

## 4. STUDY POPULATION SELECTION

### 4.1 Study Population

Adult subjects aged 18 years and older are eligible to be enrolled into this study. Subjects should have a current diagnosis of POAG or OHT. POAG in one eye and OHT in the other is acceptable. Subjects may be treatment-naïve or taking prescribed ocular hypotensive therapy at the time of screening. However if currently on ocular hypotensive treatment, they must discontinue from it for the duration of the study, and follow a prescribed washout period depending on the class of medication they are taking (see [Table 1](#)). Further details regarding subject eligibility are provided below (Sections 4.2 and 4.3).

Approximately 2 sites in the USA will participate in the study.

### 4.2 Inclusion Criteria

Subjects have to meet all of the following criteria at screening and qualification visits to enter into the study:

1. Must be 18 years of age or older
2. Diagnosis of POAG or OHT in both eyes (OAG in one eye and OHT in the fellow eye is acceptable)
3. Unmedicated (post-washout, or treatment-naïve) IOP >20 mmHg and <30 mmHg in both eyes at 08:00 hours, and >17 mmHg but <30 mmHg at 13:00 and 16:00 hours at the qualification (Day 1, baseline) visit
4. Corrected visual acuity in each eye +1.0 on the logMAR scale or better by ETDRS chart or its equivalent in each eye (equivalent to 20/200 or better Snellen visual acuity in each eye)
5. Be able and willing to provide signed informed consent and follow study instructions

### 4.3 Exclusion Criteria

Subjects meeting any of the following criteria during screening or qualification evaluations (eg, at the time of randomization) will be excluded from entry into the study:

#### Ophthalmic:

1. Clinically significant ocular disease (eg, corneal edema, uveitis, severe keratoconjunctivitis sicca) which might interfere with interpretation of the study efficacy endpoints or with safety assessments, including subjects with glaucomatous damage so severe that washout of ocular hypotensive medications for one month is not judged to be safe by the Investigator

2. Pseudoexfoliation or pigment dispersion component glaucoma, history of angle closure glaucoma, or narrow angles (as assessed by the Investigator, e.g. Grade 2 or less, Shaffer Scale). Note: Previous laser peripheral iridotomy is NOT acceptable
3. Intraocular pressure  $\geq 30$  mmHg (unmedicated) in either eye (individuals who are excluded for this criterion are not allowed to attempt requalification)
4. A difference in IOP between eyes  $>4$  mmHg (unmedicated) at any baseline time point
5. Use of more than two ocular hypotensive medications within 30 days of screening. Note: fixed dose combination medications, for the purpose of this exclusion criterion, count as two medications
6. Known hypersensitivity to any component of the formulation (eg, benzalkonium chloride, etc.), or to topical anesthetic.
7. Previous glaucoma intraocular surgery or glaucoma laser procedures in either eye
8. Keratorefractive surgery in either eye (eg, radial keratotomy, PRK, LASIK, corneal cross-linking, etc.)
9. Report of ocular trauma in either eye within the six months prior to screening, or ocular surgery or non-refractive laser treatment within the three months prior to screening
10. Recent or current evidence of ocular infection or inflammation in either eye. Current evidence of clinically significant blepharitis, conjunctivitis, or a history of herpes simplex or zoster keratitis in either eye at screening.
11. Use of ocular medication in either eye of any kind within 30 days of screening, with the exception of a) ocular hypotensive medications (which must be washed out according to the provided schedule), b) lid scrubs (which may be used prior to, but not after screening), or c) lubricating drops for dry eye (which may be used throughout the study)
12. Mean central corneal thickness greater than 620  $\mu\text{m}$  in either eye at screening
13. Any abnormality preventing reliable applanation tonometry of either eye (eg, keratoconus, etc.)
14. Lack of suitable episcleral vein prior to performing EVP measurements at Visit 2/Day 1 (applicable to 1 site only [Mayo Clinic])

Systemic:

15. Clinically significant abnormalities (as determined by the Investigator) in any recent (within 6 weeks prior to screening) laboratory tests at screening which may affect the study results. Laboratory assessments, other than pregnancy tests in females of child-bearing potential and vital signs, will not be conducted for this study

16. Clinically significant systemic disease (eg, uncontrolled diabetes, myasthenia gravis, hepatic, renal, endocrine or cardiovascular disorders) which might interfere with the study
17. Participation in any investigational (interventional) study within 60 days prior to screening
18. Changes of systemic medication that could have an effect on IOP within 30 days prior to screening, or anticipated during the study, including use of any steroid-containing drug regardless of route of systemic administration (eg, steroid inhalers)
19. Women of childbearing potential who are pregnant, nursing, planning a pregnancy, or not using a medically acceptable form of birth control. An adult woman is considered to be of childbearing potential unless she is one year post-menopausal or three months post-surgical sterilization. All females of childbearing potential must have a negative pregnancy test result at the screening examination and must not intend to become pregnant during the study

## **5. STUDY TREATMENTS**

### **5.1 Description of Treatments**

#### **5.1.1 Investigational Product**

Netarsudil ophthalmic solution 0.02% is a sterile, isotonic, buffered aqueous solution containing netarsudil mesylate (0.02%), boric acid, mannitol, water for injection, and preserved with benzalkonium chloride (0.015%). The product formulation is adjusted to approximately pH 5.

#### **5.1.2 Placebo**

Netarsudil ophthalmic solution 0.02% placebo is a sterile, isotonic, buffered aqueous solution containing boric acid, mannitol, water for injection, and preserved with benzalkonium chloride (0.015%). The product formulation is adjusted to approximately pH 5.

#### **5.1.3 Treatments of Subjects**

Enrolled subjects will receive both investigational products (IPs), Netarsudil Ophthalmic Solution 0.02% (QD AM) and Netarsudil Ophthalmic Solution Placebo (QD AM). Individual eyes will be randomized to receive active treatment or placebo; one treatment will be dosed in the right eye (OD), and the other treatment will be dosed in the left eye (OS). Each IP dose will be self-administered by the study subjects. For subjects deemed unable to self-administer the doses at the qualification visit (Visit 2, Day1), a guardian or caregiver will be asked to administer the medication.

### **5.2 Selection and Timing of Dose for Each Patient**

Masked kits containing identical bottles of IP labelled “right eye” or “left eye” will be provided to all subjects at the end of Visit 2 (Day 1, qualification, baseline). They will be instructed to begin self-administration in the morning of Day 2 at approximately the same time each day (between 08:00 and 10:00 hours) for the following 6 days, returning to the site on Day 8 where study personnel will administer the final dose.

### **5.3 Method of Assigning Patients to Treatment Groups**

A randomization schedule will be prepared by an independent individual (unmasked personnel) who is not involved in the day-to-day conduct of the study. Randomization will be stratified by site using permuted blocks, such that there will be an approximately equal number of subjects assigned to each of the two sequences ([Active Left Eye and Placebo Right Eye] and [Active Right Eye and Placebo Left Eye]) at each site.

The randomization schedule will be provided to the investigational site. The eligible subjects will be assigned a randomization number at the end of Visit 2, Day 1. Randomization numbers will be assigned sequentially to subjects in the order in which they become eligible

for randomization. The site staff will dispense to the subject the study kit labeled with the corresponding randomization number. Each subject kit will contain one bottle of each product labeled “RIGHT EYE” (OD) and “LEFT EYE” (OS). The randomization number will be recorded on the subject’s source document and electronic case report form (eCRF).

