#### **5.4 Masking**

The study is designed as double-masked for the duration of the study. Assignment to treatment with netarsudil ophthalmic solution 0.02% or placebo will be randomized. The container-closure systems for both treatments are identical to preserve masking.

Given the nature of this study design, each subject will receive 2 bottles of masked medication, one labelled “right eye” and one labelled “left eye”. The final (7th) dose will be administered at the clinical site by study personnel, after all of the 08:00 hour procedures and measurements have been performed.

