## 5.8 Packaging and Labeling

The container-closure systems for the investigational products are identical. The products for each individual treatment assignment will be packaged into identical subject kits; each subject kit will contain two bottles: one each of Netarsudil Ophthalmic Solution 0.02% and Netarsudil Ophthalmic Solution Placebo.

Each packaged unit will be labeled with an investigational label with the following minimal information: the study number, kit number, right/left eye designation, and storage statement, including a statement “Caution - New Drug - Limited by Federal (US) Law to Investigational Use” or equivalent.

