## **6.5 Dispensing Investigational Product**

Study staff responsible for dispensing IP will be listed on the Delegation of Responsibilities log. When a subject meets all criteria for selection and has completed all screening and qualification assessments, the subject will be randomly assigned masked treatment to one eye (left eye or right eye) and masked placebo assigned to the contralateral eye, according to the randomization schedule (Section [5.3](#)). IP will be then dispensed to randomized subjects at the end of Visit 2 (Day 1), and subjects will be instructed to begin dosing the following morning (Day 2). The responsible study staff will account for all used and unused IP kits and their contents by maintaining an IP accountability log.

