### **10.6 Study Monitoring**

Clinical research associates hired or contracted by the Sponsor will be responsible for monitoring the study sites and study activities. They will contact and visit the Investigator regularly. The actual frequency of monitoring visits depends on subject enrollment and on study site performance. Among others, the following items will be reviewed:

- study progress
- compliance with the protocol
- completion of eCRFs
- dispensing, storage, and accountability of IP, including unmasking of IP
- source data verification
- AE and SAE reporting
- essential documents contained within the regulatory binder

For source data verification (i.e., comparison of eCRF entries with subject records), data will be 100% source verified and will include, but not be limited to: subject identification, informed consent and assent, if applicable (procedure, signature, and date), selection criteria, and primary efficacy and safety parameters (i.e., AEs).

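### Does giving the site the randomization schedule undo the masking of the eye assignments?

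*Protocol*

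**What the plan says.** Protocol 5.3 describes a schedule "prepared by an independent individual (unmasked personnel) who is not involved in the day-to-day conduct of the study". It is stratified by site, uses permuted blocks, and allocates subjects to one of two sequences: active in the left eye with placebo in the right, or the reverse. The next paragraph opens with "The randomization schedule will be provided to the investigational site". It then says that eligible subjects receive randomization numbers in sequence, and that "The site staff will dispense to the subject the study kit labeled with the corresponding randomization number". SAP 4.1 carries the same text.

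Protocol 5.4 states: "The study is designed as double-masked for the duration of the study". The means it names is that the two products come in identical containers; it does not discuss who holds the schedule. Protocol 6.5 has masked treatment assigned to one eye and "masked placebo assigned to the contralateral eye, according to the randomization schedule".

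**The concern.** The plan mentions only one schedule, and that schedule fixes which eye is active. When the following paragraph sends the schedule to the site, the natural grammatical reference is to that same document. No available passage says that the site's copy is cut down to numbers, is sealed, or goes only to an unmasked holder. Taken literally, the plan keeps the person who prepares the schedule away from the conduct of the trial and then hands the result to those who conduct it.

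Masking matters here. The primary test is a one-sided paired comparison of the two eyes of each subject. Site personnel instil the last dose on Day 8, and outflow facility is measured at the site at 13:00 and 16:00 that day. Someone who knew the active eye could shift the readings of one eye against the other, and that shift would go straight into the treatment difference. Selection bias is less of a worry, because every subject receives both treatments and both eyes must qualify.

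**Working it through.** The point depends on no numeric input, so the check is to set the passages side by side and see which reading they support.

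1. **What the sentence is for.** In Protocol 5.3 it introduces the paragraph on numbering and dispensing. The steps that follow need only the next number and the kit that carries it. Nothing the site does with the schedule requires the eye assignment.
2. **Who may know the assignments.** The same section gives preparation of the schedule to someone it labels unmasked and places outside daily conduct. That separation would serve no purpose if the site then received the full key.
3. **What the site handles.** Protocol 5.2 provides "Masked kits containing identical bottles of IP labelled" for the right or the left eye. Appendix 3 has the sponsor supply medication that is masked and coded. Protocol 6.5 ties the schedule to masked treatment and masked placebo, so it describes a schedule operated under masking.
4. **How unmasking is treated.** Protocol 10.6 has monitors review "dispensing, storage, and accountability of IP, including unmasking of IP", and Protocol 10.7 keeps unmasking documentation among the study records. Both treat unmasking as an event to be recorded. Neither would make sense if the site knew the assignments from the start.
5. **When the codes are opened.** Protocol 9.3.2 and SAP 7.2 require a masked judgement of protocol violations before unmasking. SAP 6 lists the unmasking of treatment codes with database lock and the settling of analysis populations, as steps that precede the final analyses.

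All five point to a list of numbers at the site, with the key held elsewhere. Only the unqualified wording of the one sentence points the other way.

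**Effect on the plan's figures.** The sample-size statement can be reproduced without reference to the schedule:

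- SD of the paired difference = √(2 × 0.06² × (1 − 0.4)) = 0.0657, which the plan rounds to 0.07.
- One-sided paired t-test, n = 16, difference 0.08, α = 0.05: power 0.9966 with SD 0.07 and 0.9986 with SD 0.0657. Both agree with the stated figure of more than 95%.
- 16 / (1 − 0.20) = 20 subjects to be randomized.

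Rewording the sentence would change none of these.

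**The case for a change.** The strongest case for a change is that custody of the allocation list should not be left to inference. The supporting passages make the masked reading likely, but none states it, and one sentence in each document would settle it at almost no cost. It is true that the express statement is absent, and adding it would do no harm. It would, however, only write down what the rest of the plan already requires. A site given the full key would be in breach of Protocol 5.4 whatever Protocol 5.3 says.

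Three further arguments do not stand.

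- **Kit labels.** Protocol 5.3 has the kit carry the randomization number, while Protocol 5.8 lists "the study number, kit number, right/left eye designation, and storage statement". Protocol 5.8 presents this as the minimum content, so it does not exclude a randomization number, and the two numbers may be the same.
- **Unmasking route.** The available text describes no procedure for unmasking. Section 10.1 and the procedures in Appendix 2 are not available in the text reviewed, so a gap in the plan cannot be inferred.
- **Inflated type I error.** One can assume a difference in reading between the eyes and calculate a higher false-positive rate. The documents give no size for such a bias. The calculation would also need the site's copy to show the assignments and the person measuring to have seen it, and the documents show neither. The same rate would follow from any other cue to the active eye, so it does not measure the effect of this sentence.

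**Conclusion.** The concern does not call for a change. The wording in Protocol 5.3 and SAP 4.1 is ambiguous, but it does not establish a conflict with the double-masked design. Analysts and site staff following the whole plan would work with masked kits and numbers, with the key kept by the independent unmasked person until the codes are opened. The effect on the plan's figures is nil, and the effect on the result is nil so long as the masking required by Protocol 5.4 is followed.

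This rests on reading the sentence with its surrounding sections. It is a conclusion about the plan as written; the documents cannot show what each site was actually sent, which is a matter of trial conduct.
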